6.18. IP Accountability

All IP that is dispensed during the course of the study will be reconciled and accounted for by the Investigator (or designee). Applicable information such as lot number, date dispensed, numbers of capsules or vials dispensed, date returned, the number of capsules returned, or number of vials returned should be collected as well as information provided by the subject or the caregiver (eg, subject dosing diary). IP accountability should be completed on Cycle 1 Day 1, at the end of every treatment cycle (eg, on Day 1 of Cycle 2, Day 1 of Cycle 3), at the end of every cycle in the OEP if treatment continues beyond 12 cycles, and at the Treatment Discontinuation Visit.

6.19. Information to be Collected on Screen Failures

The informed consent date, demographics, reason subject did not qualify for the study and the Investigator's signature will be collected for all subjects determined to be screen failures. If the reason for the screen failure is an AE, the AE and concomitant medications used to treat the AE will be recorded on the CRF and captured in the subject's source documents from the date of signing informed consent to the day the subject is confirmed to be a screen failure. Relevant information will also be recorded on the Screening Log.

6.20. Treatment Activity

The primary endpoint consists of the assessment of the morphologic complete response rate within the first 4 cycles of study treatment with lenalidomide. Morphological complete response is defined as CR or CRi. These response criteria will be determined using the revised AML IWG criteria (Cheson, 2003) (Appendix D).

6.20.1. Bone Marrow Aspirate or Biopsy and Peripheral Blood

To determine morphologic CR/CRi, BMA/biopsy and peripheral blood smear must be collected from all subjects at screening and at the completion of the 21-day treatment period of the predefined treatment Cycles 1, 2, 3 and 4 within 6 days **before dosing for each subsequent cycle** (ie, between Day 22 to Day 27 of that cycle) (Table 2). If morphologic CR/CRi is achieved within the first 2 cycles, BMA/biopsy and peripheral blood smear will not be required at the end of Cycle 3. For all subjects, BMA/biopsy and peripheral blood smear must be performed at the completion of Cycle 4, and at the Treatment Discontinuation Visit or at the time of suspected relapse (whichever occurs first). For subjects who are assessed as having partial response, the BMA/biopsy and peripheral blood smear will be repeated at Cycle 8 unless the subject goes to allogeneic HSCT, and at the Treatment Discontinuation Visit or at the time of suspected treatment failure (whichever occurs first). ***A bone marrow biopsy is required only if a bone marrow aspirate cannot be obtained.*** Subjects demonstrating clinical benefit as per the Investigator at the end of Cycle 4 and beyond may continue to receive lenalidomide on study for up to 12 cycles in the absence of protocol-defined toxicity or transitioning to allogeneic HSCT.

In the case where a study center has an IRB- and Celgene-approved procedural ICF/IAF that allows collection of additional bone marrow samples for potential research purposes, the latest pre-study PB and BM aspirate/biopsy may be used for screening study assessments.

The screening BMA slide (and/or bone marrow biopsy paraffin embedded slide) and peripheral blood smear slide **must** be provided to the central reviewers at [REDACTED]. The central review [REDACTED] will provide standardized analysis and reporting for all subjects. The central reviewer's assessment will be used retrospectively to confirm diagnosis.

In addition, BMA/biopsy will be obtained to confirm CR, CRi, partial remission (PR), or treatment failure, as assessed by the Investigator based on complete blood count [CBC] with white blood cell (WBC) differential results (defined in Appendix D). Morphological response will be assessed based on peripheral blood count recovery and morphologic assessment of

BMAs/biopsies (Table 2). Assessments to be collected during the Follow-up Phase will include new anticancer therapies, HSCT, SPMs, SAEs, [REDACTED].

For screening assessments, instructions for submission of pathology data (flow cytometry, reports of cytogenetics and FISH) to [REDACTED], central reviewer, are provided in Appendix I.

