An external DMC will evaluate safety and treatment activity data in an ongoing and periodic manner to assess benefit-to-risk considerations throughout the study. The function of the DMC is to monitor the safety and activity of the study treatment. Once 4 subjects having received at least one dose of lenalidomide have completed at least 1 cycle of study treatment or discontinued treatment (whichever occurs first), the DMC will evaluate the safety data available and provide a recommendation. The DMC will also provide recommendations about the continuation of the study from Stage 1 to Stage 2 (continue as planned, continue with modifications or stop treatment and/or enrollment) and advise on ways to improve quality. The underlying principles for the DMC are ethical and safety aspects for the subjects. It will be the task of the DMC to examine whether the conduct of the study is still ethically justifiable, whether security of the subjects is ensured, and whether the process of the study is acceptable. For this, the DMC has to be informed about the adherence to the protocol, the subject accrual, and any observed AE(s). The composition and responsibilities of the DMC, including the structure and procedures of its meetings, will be outlined in a DMC charter.

The study consists of 3 phases: Screening Phase, Treatment Phase and Follow-up Phase.

Screening Phase

The Screening Phase will start from the time of signing the informed consent form (ICF)/informed assent form (IAF) and will last no more than 14 days, at which time the Treatment Phase will begin (Cycle 1 Day 1). Subject's screening procedures are to occur during the Screening Phase within 14 days prior to dosing on Cycle 1 Day 1.

As part of the screening procedures, a fresh bone marrow aspirate and/or a bone marrow biopsy paraffin embedded slide will be collected from all subjects for confirmation of disease. The confirmation of disease will be performed locally.

A standard cytogenetic metaphase preparation from the fresh BMA must be prepared for the cytogenetic testing/chromosome analysis including karyotype. The local site will submit the reports of the karyotype, FISH studies, as well as any available data on molecular mutations (FLT3, CEPBa, NPM1, and others including exome sequencing via Foundation Medicine or other sources) if performed, to the central reviewer at [REDACTED]. If subjects have a FISH detectable marker, the test should be repeated until CR/CRi and at relapse.

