- ^k All concomitant over-the-counter/prescription medications/procedures, and intravenous medications taken from signing of the informed consent up to 28 days after the last dose of lenalidomide must be recorded on the appropriate CRF.
- ^l Lenalidomide should be dispensed on Day 1 of each cycle. Only enough lenalidomide for 1 cycle of therapy will be dispensed with each cycle of therapy. The first dose of lenalidomide should be taken only after all Day 1 procedures have been completed with the exception of the collection of PK sampling.
- ^m Lenalidomide accountability should be assessed before IP dispensing for each treatment cycle.
- ⁿ A fresh bone marrow aspirate (and/or a fresh bone marrow biopsy paraffin embedded slides) will be collected at screening from all subjects for confirmation of relapsed/refractory disease.
- ^o ***A bone marrow biopsy is required only if a bone marrow aspirate cannot be obtained.***
- ^p A standard cytogenetic metaphase preparation from the fresh BMA must be prepared for the local cytogenetic testing/chromosome analysis including karyotype. The local site will submit the reports of the karyotype, FISH studies, as well as any available data on molecular mutations (FLT3, CEPBA, NPM1, and others including exome sequencing via Foundation Medicine or other sources) if performed to the central reviewer for retrospective review at Screening only. If subjects have a FISH detectable marker, the test should be repeated until CR/CRi and at relapse.

- ^q The screening BMA slide (and/or bone marrow biopsy paraffin embedded slide) and peripheral blood smear slide **must** be provided to the central reviewers at the [REDACTED]. The central review [REDACTED] will provide standardized analysis and reporting for all subjects. The central reviewer's assessment will be used retrospectively to confirm diagnosis. In the case where a study center has an IRB- and Celgene-approved procedural ICF/IAF that allows collection of additional bone marrow samples for potential research purposes, the latest pre-study PB and BM aspirate/biopsy may be used for screening study assessments.

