6.1. Screening, Study Entry and Treatment Procedures

Pediatric subjects from 1 to ≤ 18 years of age with rrAML will be considered for participation in this study. The subject(s) and/or guardian(s) (as appropriate by local law and regulations) will be provided with a written ICF or IAF, given the opportunity to ask any questions concerning the study and will sign an ICF or IAF prior to participating in any study procedures.

All subjects who sign an ICF/IAF or children of parents and/or guardians who sign the parental consent must be screened into the IWRS immediately upon signature.

After giving written informed consent/informed assent, subjects will undergo screening assessments to be assessed for study eligibility. Subjects who do not meet the eligibility criteria or who withdraw (for any reason) during the Screening Phase will be considered screen failures (sites should log onto the IWRS immediately to screen fail the subject in the system). Study-specific medical procedures to confirm eligibility are to be performed after signing ICF/IAF and must take place within 14 days prior to Cycle 1 Day 1.

Subjects who fail screening may be rescreened at any time, and as considered appropriate, at the Investigator's discretion. For subjects who are rescreened, a new ICF/IAF will need to be signed and screening procedures will need to be repeated if originally more than 14 days prior to the rescreen date.

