7.3. Exclusion Criteria

The presence of any of the following will exclude a subject from enrollment:

1. Subject has Down syndrome.
2. Subject has French-American-British classification (FAB) type M3 leukemia (acute promyelocytic leukemia) or identification of t(15;17).
3. Subject has isolated CNS involvement or extramedullary relapse. (Subjects with combined CNS/marrow relapse may be enrolled).
4. Subject has had prior treatment with cytotoxic chemotherapy within 2 weeks of the first dose of lenalidomide with the exception of hydroxyurea (allowed prior to the first dose of lenalidomide and through Day 14 of Cycle 1) and intrathecal (IT) cytarabine will be administered within 2 weeks prior to administration of lenalidomide.
5. Subject has had prior treatment with biologic antineoplastic agents less than 7 days before the first dose of lenalidomide. For agents that have known AEs occurring beyond 7 days after administration (ie, monoclonal antibodies), this period must be extended beyond the time during which acute AEs are known to occur.
6. Subject has had prior treatment with lenalidomide.
7. Subject is pregnant or lactating.
8. Subject has an uncontrolled systemic fungal, bacterial, or viral infection (defined as ongoing signs/symptoms related to the infection without improvement despite appropriate antibiotics, antiviral therapy, and/or other treatment).
9. Subject has known Human Immunodeficiency Virus (HIV) positivity (subjects who are receiving antiretroviral therapy for HIV disease).
10. Subject has a prior history of malignancies other than AML unless the subject has been free of the disease for ≥ 5 years from first dose of lenalidomide.
11. The presence of any of the following will exclude a subject from enrollment:
 - Subject has any significant medical condition, laboratory abnormality, or psychiatric illness that would prevent the subject from participating in the study.

- Subject has any condition including the presence of laboratory abnormalities, which places the subject at unacceptable risk if he/she were to participate in the study.
 - Subject has any condition that confounds the ability to interpret data from the study.
12. Subject has cardiac disorders (Common Terminology Criteria for Adverse Events [CTCAE] version 4.03 Grade 3 or 4).
 13. Subject has a history of well-documented prior veno-occlusive disease (VOD).

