1. JUSTIFICATION FOR AMENDMENT

Significant changes included in this amendment are summarized below:

- The Medical Monitor/Emergency Contact Information section was updated.
- Duration of response was added as a secondary endpoint [REDACTED] (Protocol Summary, Sections 2.2, 3.2, 10.6.2).
- Updated the number of study sites from 75 to 70 to better reflect the number of sites involved with the study (Protocol Summary, Sections 4.1, 7.1, 12.2).
- Provided clarification language to state the DMC will evaluate available safety data and provide a recommendation once 4 subjects having received at least one dose of lenalidomide have completed at least 1 cycle of study treatment or discontinued treatment (whichever occurs first) (Protocol Summary, Sections 4.1, 4.4, 10.9).
- Amended the word ‘banked’ to ‘stored’ in regard to the central biorepository samples in order to clarify how samples will be handled (Protocol Summary, Sections 4.1, 5, 6.27).
- Language was added to introduce the lenalidomide oral suspension (in addition to capsule formulation). The development of the oral suspension and implementation in the study is a key binding element of the pediatric Written Request for lenalidomide. The oral suspension is available for use in subjects who are unable to swallow the capsule formulation or at the discretion of the investigator (Protocol Summary, Sections 1.3, 8.1, 8.2, 19).
- Amended language to state the pregnancy test 10 to 14 days prior to initiation of lenalidomide may be omitted, at the discretion of the investigator, for any FCCBP/FCBP who has high acuity disease requiring immediate treatment with lenalidomide. This change was made to recognize that potential subjects identified for enrollment into the study may have high acuity AML disease and may necessitate immediate treatment with lenalidomide. The pregnancy test within 24 hours prior to the first dose of lenalidomide is still required to be performed (Sections 5, 6.8, 7.2).
- Added language to allow use of pre-study PB and BM aspirate/biopsy results for screening study assessments in the case where a study center has an IRB- and Celgene-approved procedural ICF/IAF that allows collection of additional bone marrow samples for potential research purposes. This update was made to recognize that performing additional PB and BM assessments at screening may not be feasible for certain subjects (Sections 5, 6.5, 6.20.1, 14.3).

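### At centers with a procedural consent, the pre-study marrow that may replace the screening marrow has no stated maximum age and need not follow the last antileukemic therapy, so a remission from prior chemotherapy could count as a lenalidomide CR/CRi

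*Protocol*

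**What the plan says.** **Default rule.** Protocol 4.1 states: "Subject's screening procedures are to occur during the Screening Phase within 14 days prior to dosing on Cycle 1 Day 1". Protocol 6.1 says that study-specific procedures to confirm eligibility come after consent and "must take place within 14 days prior to Cycle 1 Day 1". Table 2, note n, adds: "A fresh bone marrow aspirate (and/or a fresh bone marrow biopsy paraffin embedded slides) will be collected at screening from all subjects".

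**Exception.** Protocol 6.20.1 opens with a condition, "In the case where a study center has an IRB- and Celgene-approved procedural ICF/IAF" (one that allows extra marrow samples for research), and then says that "the latest pre-study PB and BM aspirate/biopsy may be used for screening study assessments". The same exception stands in Table 2 note q, in 6.5 (confirmation of relapse) and in 14.3 (consent). None of the four places gives an age limit or refers to the last therapy. The amendment rationale is that "performing additional PB and BM assessments at screening may not be feasible for certain subjects".

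**Washout.** Exclusion 4 (Protocol 7.3) bars a child if "Subject has had prior treatment with cytotoxic chemotherapy within 2 weeks of the first dose of lenalidomide", with hydroxyurea and intrathecal cytarabine excepted. Exclusion 5 sets 7 days for biologic antineoplastic agents, longer for agents with late adverse events.

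**Rescreening.** Protocol 6.1 says that "screening procedures will need to be repeated if originally more than 14 days prior to the rescreen date".

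**Endpoint.** Inclusion 3 requires at least 5% marrow blasts and gives no date for the sample. Protocol Appendix D defines CR and CRi by a marrow under 5% blasts with trilineage hematopoiesis and no extramedullary disease. Under Protocol 10.6.1 and SAP 10.1, one CR/CRi at the end of any of Cycles 1 to 4 counts, even if it is later lost.

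**The concern.** In a single-arm trial against a fixed 10% reference, a CR/CRi can be credited to lenalidomide only if leukemia was present in the marrow when dosing began. The default rules secure this for cytotoxic chemotherapy: a marrow taken in the last 14 days cannot precede a dose given more than 14 days ago. The exception removes that guarantee for one kind of subject, a child at an excepted center who has had no marrow since the last block.

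No later step would reveal the problem. Central review confirms the diagnosis from the same screening slide. SAP 5.1 takes as baseline the latest value on or before the first dose, whatever its age. Neither the Response Rate population (Protocol 10.2, SAP 5.3.2) nor the primary analysis (SAP 10.1) has a rule on the marrow date. Such a remission would count toward both the 3-of-18 and the 8-of-43 decisions.

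**Working it through.** **1. Does the text allow it?** Take a child at an excepted center whose latest marrow shows relapse, who then receives a block ending 14 days before Cycle 1 Day 1, and who has no further marrow.

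- The old marrow is the latest pre-study sample and satisfies the undated 5% criterion.
- The 14-day sentence in 6.1 is written for study-specific procedures done after consent. A pre-study marrow is neither, and no sentence extends the window to it.
- The first response marrow falls on Day 22 to 27 of Cycle 1, that is 14 + 21 = 35 to 14 + 26 = 40 days after the last cytotoxic dose.
- If the block produced a remission with under 5% blasts, trilineage hematopoiesis and no extramedullary disease, that marrow meets the CR or CRi marrow criteria.

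For biologic agents the window alone would not be enough. A marrow on Day -12 can precede an agent given on Day -7.

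**2. The plan's own figures.** Inputs from Protocol 10.3: 18 + 25 = 43 subjects, continue at 3 or more of 18, declare activity at 8 or more of 43, rates 10% and 25%.

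P(declare) = Σ over x = 3 to 18 of P(X1 = x) × P(X2 ≥ 8 − x), with X1 ~ Bin(18, p) and X2 ~ Bin(25, p).

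This gives 0.0480 at p = 0.10 and 0.8003 at p = 0.25. The design reproduces. The chance of passing Stage 1 at p = 0.10 is 0.266.

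**3. One misattributed responder in Stage 1, true rate 10%.** No contamination rate is needed; the result is conditional on one such case. The other 17 must supply at least 2 responders:

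P(pass Stage 1) = 1 − 0.9^17 − 17 × 0.1 × 0.9^16 = 1 − 0.1668 − 0.3150 = 0.518.

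P(declare) = Σ over x = 2 to 17 of P(Bin(17, 0.1) = x) × P(Bin(25, 0.1) ≥ 7 − x) = 0.109.

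With one such responder in each stage, P(declare) is 0.191.

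**4. Illustrative contamination.** Let f be the share of subjects who enter on a marrow older than their last therapy, and c the chance that this therapy yields a CR/CRi by the end of Cycle 4. Neither is in the documents; both are assumptions. The observed rate is 0.10 + 0.90 × f × c.

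| f | c | Observed rate | P(declare) |
|---|---|---|---|
| 0 | – | 0.1000 | 0.048 |
| 2% | 20% | 0.1036 | 0.057 |
| 5% | 10% | 0.1045 | 0.059 |
| 10% | 20% | 0.1180 | 0.103 |
| 20% | 20% | 0.1360 | 0.182 |
| 20% | 30% | 0.1540 | 0.282 |

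If the true lenalidomide rate were 5%, P(declare) would be 0.0009 without contamination and 0.025 at f = 20%, c = 20%, still below the nominal 5%.

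**The case against.** **The 14-day window may still apply.** The exception turns on a different consent form and is repeated in the consent section. It can be read as relaxing only the requirement to sample after consent. On that reading the cytotoxic route closes. This reading is open, but the protocol does not state it, and the amendment rationale, that new sampling may not be feasible, leans the other way. What stands is an ambiguity that has to be reconciled.

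**The exception is narrow.** It applies only at centers with the approved procedural consent. The word latest also means that a marrow taken after the last therapy, where one exists, is the one to use. Both points stand and limit f. A reader who sees only the sentence on the pre-study marrow might infer a general waiver for all sites; the opening condition rules that out.

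**A marrow emptied by chemotherapy is not a CRi.** A reader might infer that under 5% blasts with low counts is enough. Appendix D also requires trilineage hematopoiesis and no extramedullary disease, so an aplastic marrow does not qualify. Only a true remission from the earlier block is at issue.

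**There are partial safeguards.** Inclusion 7 requires recovery from acute effects of prior chemotherapy, with toxicities at Grade 2 or lower. Protocol 8.3 has the sponsor verify eligibility. Protocol 6.5 asks for at least two recorded relapse or refractory dates. Blood blasts are counted on Cycle 1 Day 1. These lower the risk, but none requires marrow disease after the last therapy.

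**Rescreening.** A reader might infer that a reused procedure may be 14 + 14 = 28 days old at dosing. The 14-day limit to Cycle 1 Day 1 in the same section has no carve-out for rescreening, and both limits can apply together. The two anchors need reconciling; 28 days is not a firm allowance.

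**Conclusion.** The gap is real but restricted to excepted centers and to subjects with no marrow since their last therapy. Within that group the text permits a remission from earlier chemotherapy to be counted for lenalidomide. How often this would happen cannot be known from the documents.

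The firmest figure is conditional on a single case: one such responder in Stage 1 at a true 10% rate moves the chance of passing Stage 1 from 0.266 to 0.518 and the false-positive rate from 0.048 to 0.109. The range of about 0.057 to 0.28 rests wholly on the assumed f and c. A reader might take its upper part as the expected inflation; the documents support no particular value, and at the low end the effect is negligible.

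The stated sample size, alpha and power are correct. This is an inexpensive improvement that protects attribution in a go/no-go trial; it is not a fault in the design calculation.

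**What to change.** 1. In Protocol 6.5, 6.20.1, 14.3 and Table 2 note q, state that a pre-study marrow qualifies only if it was taken within the 14-day window before Cycle 1 Day 1 and after the last antileukemic therapy, hydroxyurea and intrathecal cytarabine excepted. Both conditions are needed because of the 7-day biologic washout. In 6.1, reconcile the rescreening sentence with the Cycle 1 Day 1 anchor.
2. Record the date of the baseline marrow against the date of the last therapy. In SAP 10.1, add a sensitivity analysis of the primary rate, and of the 3-of-18 and 8-of-43 counts, that treats any CR/CRi without a post-therapy baseline marrow as a non-response.

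**Effect.** With every baseline marrow taken after the last therapy, f = 0 and the design returns to 43 subjects, alpha 0.0480 and power 0.8003. A late effect of earlier therapy, or of hydroxyurea through Day 14 of Cycle 1, could still contribute to a response.

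**Cost.** The change to the entry rule is not free. Some children at the excepted centers would need the scheduled screening marrow, and the amendment rationale says that resampling may not be feasible for all. The sensitivity analysis alone needs no new procedure: Protocol 6.4 and 6.15 already call for prior AML therapy and medication dates, and SAP 10 already lists the screening marrow.
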